5.4 Receiving & Storage

Choline bitartrate and phosphatidylcholine supplements will be obtained from a commercial source and stored at room temperature in a dry location. They will be kept locked in a secure location. Temperature will be monitored and recorded weekly to make sure that the temperature remains between 15° and 30° Celsius.

Whole, hardboiled, peeled eggs will be obtained from a commercial source and stored in a refrigerator, which will be monitored to ensure that the temperature remains under 5°C. Eggs will not be stored longer than two weeks.

5.5 Dispensing Study Drug

The supplements will be dispensed directly to the subject by the study coordinators or other study personnel. The number of supplements given at each visit will be recorded on a drug accountability record. This form will contain a running log of supplements received and given out. Any supplements inadvertently dropped or damaged will be logged and destroyed. All entries in the log will be dated and initialed by study staff.

5.6 Return and Destruction of Study Drug

At the completion of the study or, if a subject withdraws early, at their final visit, any remaining choline supplements will be returned to the study coordinator. The supplements returned, if any, will be recorded on the drug accountability record. Any discrepancies will be investigated and resolved prior to the destruction of any supplements. Returned supplements will be destroyed on site and their destruction will be documented.

6.0 STUDY PROCEDURES

This is a prospective pilot study consisting of 5 arms. Up to 100 subjects will be enrolled across all arms in this pilot study, with a goal of having at least 10 subjects complete each arm of the study.

Arm 1: Choline Bitartrate Tablets Alone

Subjects in this arm will be asked to take two 500mg choline bitartrate tablets (for a total of 1,000mg) daily by mouth for four weeks. They will be asked to take one capsule in the morning and one in the evening. We aim to have at least 10 subjects complete this arm.

Arm 2: Whole Hardboiled Eggs

Subjects in this arm will be asked to eat four hardboiled eggs daily for four weeks. They will be asked to eat 2 eggs in the morning and 2 eggs in the evening. We aim to have at least 10 subjects complete this arm.

Arm 3: Whole Hardboiled Egg + Choline Bitartrate Tablets

Subjects in this arm will be asked to eat four hardboiled eggs and take two 500mg choline bitartrate tablets (for a total of 1,000mg) by mouth daily for four weeks. They will be asked to eat 2 eggs and take 1 capsule in the morning, and then eat 2 eggs and take 1 capsule in the evening. We aim to have at least 10 subjects complete this arm.

Arm 4: Egg Whites + Choline Bitartrate Tablets

Subjects in this arm will be asked to eat the equivalent of four egg whites and take two 500mg choline bitartrate tablets (for a total of 1,000mg) by mouth daily for four weeks. They will be asked to eat 2 egg whites and take 1 capsule in the morning, and then eat 2 egg whites and take 1 capsule in the evening. We aim to have at least 10 subjects complete this arm.

Arm 5: Phosphatidylcholine Capsules Alone

Subjects in this arm will be asked to take six 420 mg choline bitartrate tablets (for a total of 2,025 mg) daily by mouth for four weeks. They will be asked to take three capsule in the morning and three in the evening. We aim to have at least 10 subjects comlete this arm.

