3.0 STUDY DESIGN

This is a prospective non-blinded randomized study with 5 study arms as detailed below. For each study arm, subjects will be asked to consume choline bitartrate tablets, phosphatidylcholine capsules, and/or eggs or egg whites every day for 4 weeks.

Arm 1: whole hardboiled egg

Arm 2: choline bitartrate tablets

Arm 3: whole hardboiled egg + choline bitartrate tablets

Arm 4: egg whites + choline bitartrate tablets

Arm 5: phosphatidylcholine capsules

For arms 1-4, subjects will be randomly assigned to one of these study arms at the time of enrollment. For arm 5, the phosphatidylcholine arm, which we have added in version 1.2 of this protocol, subjects will not be randomized but will instead be assigned this arm until at least 10 subjects have completed this arm. We expect to enroll at least 10 subjects into each of the 5 arms of the study, up to a maximum of 100 total study participants. The large anticipated maximum enrollment accounts for any subjects who may withdraw early or who may need to be withdrawn because of antibiotic usage or non-compliance during the course of the study.

At the first (baseline) study visit, subjects will have blood and urine samples collected. Subjects will then be randomized or assigned to one of the five study arms as described above.

Following randomization, or assignment in the case of arm 5, subjects will be asked to pick up their assigned study food and/or supplements each week. Spot urine collections will be collected weekly. Subjects will also be asked to provide a stool sample at the time of the spot urine collection if they are able to. The stool samples will be optional, we will not require them.

At the day 7 visit and the final visit they will have repeat blood and urine collections. After 4 weeks of supplementation, subjects will have their final study visit. This visit will occur between 26 and 30 days after their baseline visit.

	Day 1 (Baseline)	Day 2	Day 7*	Day 8	Day 14*	Day 21*	Day 28*	Final Visit (Day 29)
Informed consent	Х							
Vital signs and brief medical history	Х		Х				Х	
Fasting Blood Draw	Х		Х				Х	
Pick up eggs and/or supplements		Х	Х		Х	Х		
Spot Urine sample	Х		Х		Х	Х	Х	
Start 24 hour urine	Х		Х				Х	
Return 24-Hour Urine		Χ		Х				Х

|--|

^{*}these study visits can occur +/- 2 days from day noted

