5.2 Treatment Regimen

For subjects in arms 1, 3, and 4, 500 mg choline bitartrate tablets will be given to be taken daily by mouth. Subjects will be asked to take two tablets each day, one in the morning and one in the evening, for a total of 1,000 mg daily. Subjects in arm 2 will not receive any choline tablets.

For subjects in arms 2 and 3, four pre-peeled hardboiled eggs will be given to be taken daily by mouth, two in the morning and two in the evening. Subjects in arm 3 will be asked to eat the hardboiled eggs in addition to taking the choline bitartrate tablets.

For subjects in arm 4, four pre-peeled hardboiled eggs will be given and subjects will be instructed to eat only the egg whites while discarding the egg yolks. Subjects will be asked to eat two egg whites in the morning and two egg whites in the evening. Subjects in arm 4 will be asked to eat the egg whites in addition to taking the choline bitartrate tablets.

For subjects in arm 5, 420 mg phosphatidylcholine capsules will be given to be taken daily by mouth. Subjects will be asked to take 6 capsules each day, 3 in the morning and 3 in the evening, for a total of 2,520 mg daily. Subjects in arm 5 will not receive any hardboiled eggs.

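### Section 6.0 gives Arm 5 the wrong product (choline bitartrate, not phosphatidylcholine) and the wrong daily total (2,025 mg, not 2,520 mg)

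*Combined protocol and SAP*

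**What the plan says.** Arm 5 is described in three places in the combined protocol and SAP.

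- **Section 3.0 (Study Design)** lists it as "Arm 5: phosphatidylcholine capsules" and gives no dose. It later explains the origin of the arm: "For arm 5, the phosphatidylcholine arm, which we have added in version 1.2 of this protocol".
- **Section 5.2 (Treatment Regimen)** gives the full regimen: "For subjects in arm 5, 420 mg phosphatidylcholine capsules will be given to be taken daily by mouth". It continues "Subjects will be asked to take 6 capsules each day, 3 in the morning and 3 in the evening" and puts the daily total at 2,520 mg.
- **Section 6.0 (Study Procedures)** heads the arm "Arm 5: Phosphatidylcholine Capsules Alone". The dosing sentence beneath that heading reads "six 420 mg choline bitartrate tablets (for a total of 2,025 mg) daily by mouth for four weeks", and the next sentence gives the split: "They will be asked to take three capsule in the morning and three in the evening".

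For comparison, the Section 6.0 dosing sentence for the tablet-only arm (Arm 1 in that section) reads "two 500mg choline bitartrate tablets (for a total of 1,000mg) daily by mouth for four weeks".

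**The concern.** The Section 6.0 dosing sentence conflicts with its own heading and with two other sections on which product Arm 5 receives. It conflicts with its own count and strength, and with Section 5.2, on the daily total.

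Product identity is the purpose of this arm. Section 1.0 hypothesises that phosphatidylcholine supplements raise plasma TMAO less than a comparable amount of choline taken as the bitartrate salt, and to a similar degree as whole eggs. An Arm 5 given bitartrate could not test that. The total matters as well, because Section 1.0 intends the phosphatidylcholine capsules to supply an equivalent mass of choline. The protocol should therefore state one correct dose.

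Section 6.0 is current procedural text. A coordinator working from it alone would read the wrong compound and a total that does not add up.

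**Working it through.** **Inputs**

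| Item | Section 6.0, Arm 5 | Section 5.2, Arm 5 |
|---|---|---|
| Product in the heading | phosphatidylcholine capsules | no arm heading |
| Product in the dosing text | choline bitartrate tablets | phosphatidylcholine capsules |
| Units per day | 6 (3 + 3) | 6 (3 + 3) |
| Strength per unit | 420 mg | 420 mg |
| Stated daily total | 2,025 mg | 2,520 mg |

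**Total.** Daily total = units per day × mg per unit.

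- 6 × 420 = 2,520 mg. This reproduces Section 5.2 exactly and does not reproduce Section 6.0.
- Shortfall: 2,520 − 2,025 = 495 mg, and 495 / 2,520 = 19.6%.
- No other reading rescues 2,025 mg. 2,025 / 420 = 4.82 and 2,025 / 500 = 4.05, so it is not a whole number of either unit strength in the protocol. Six units would have to be 2,025 / 6 = 337.5 mg each, a strength given nowhere.

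**Product.** Section 5.2 gives bitartrate tablets to Arms 1, 3 and 4 only. Wherever else bitartrate tablet strength is stated (Section 5.2, and Arms 1, 3 and 4 in Section 6.0) it is 500 mg, so a 420 mg bitartrate tablet appears only in the disputed sentence. Sections 3.0 and 6.0 number Arms 1 and 2 in opposite order, but Arm 5 is the phosphatidylcholine arm in both lists, so that discrepancy does not affect this point. The words tablet and capsule are weak evidence by themselves, because Section 6.0 also calls bitartrate units capsules. The contradiction rests on the named product.

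**Likely cause (inference).** Once the spacing before mg is aligned, the Arm 1 and Arm 5 dosing sentences have 27 words each and differ in three: two/six, 500/420 and 1,000/2,025. Arm 5 was added at version 1.2, so a copied Arm 1 sentence with the product name left unchanged would explain the first error. The total looks like 2,520 with the 5 and the 0 exchanged.

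**Sentence taken literally.** Arm 5 would contain no phosphatidylcholine. Against the tablet arm's 1,000 mg, bitartrate would be 2,025 / 1,000 = 2.03 times by the stated total, or 2,520 / 1,000 = 2.52 times by count and strength.

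**The case against.** The facts are not in dispute, so the case against concerns weight.

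- **Recoverability.** Every other statement about Arm 5 points to phosphatidylcholine, and Sections 5.1 and 5.4 provide for obtaining and storing it. The section devoted to the treatment regimen is correct. On this view the error is editorial. That stands as far as the intended dose goes. It does not make a dosing instruction that names the wrong compound acceptable.
- **The literal reading is hypothetical.** The protocol describes no 420 mg bitartrate tablet. Six of the 500 mg tablets it does describe would give 6 × 500 = 3,000 mg, or 3.0 times the tablet arm's dose, which is outside the 2.03 to 2.52 range. This stands: that range is the arithmetic of the sentence as written, not an upper bound on what could be dispensed.
- **Safeguards.** Staff observe dosing at the first few visits (Section 5.3), dispense the supplements directly and keep a running log (Section 5.5), and investigate discrepancies in returns (Section 5.6). These make an unnoticed substitution less likely. However, Section 5.5 describes logging numbers of supplements and does not say that product or strength is recorded. The urine check in Section 5.3 looks for levels falling below baseline, which is not designed to tell one choline source from another.
- **The record check goes beyond the evidence.** It is a precaution, since nothing suggests misdosing, and correcting the sentence is enough to repair the document.

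**Conclusion.** The concern holds on both counts. Section 6.0 names the wrong product for Arm 5 and understates the daily total by 495 mg (19.6%). Both errors are in current text, and no other section flags or corrects the sentence.

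Taking Section 5.2 as the intended regimen rests on the agreement of count, strength and schedule between the two sections, on the Arm 5 heading, and on Section 3.0. On that reading the dose to be given is unaffected, and no design, power or analysis figure changes. The copying and digit-swap explanation is inference, and the conclusion does not depend on it. This is a should-fix drafting error: easy to see through with the whole protocol in hand, but located in an operative dosing instruction for the arm that exists to test phosphatidylcholine.

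**What to change.** Replace the Section 6.0 Arm 5 dosing phrase with: *six 420 mg phosphatidylcholine capsules (for a total of 2,520 mg) daily by mouth for four weeks*. That matches Section 5.2.

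As a one-off precaution, confirm which product and strength Arm 5 subjects received. Check product labels as well as the accountability record, since the record is described only as a log of numbers.

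The cost is one corrected sentence and one look at labels and records.

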6.1 Study Visit Procedures

- Blood Draw
- Spot Urine
- Medical History
- Medication Review
- Physical Exam including blood pressure, height, weight, and waist circumference
- 24-hour Urine Collection
- Stool Sample Collection (optional)

7.0 STATISTICAL PLAN

7.1 Sample Size Determination

Based on previous research, we calculate that a sample size of 5 in each arm will provide us with a power of 0.9 to detect a significant difference between groups at a significance level of 0.05. However, we plan to enroll at least 10 subjects in each arm in order to compensate for any unexpected occurrences or subject dropouts.

7.2 Statistical Methods

We plan to use standard descriptive statistics to characterize the overall study population and subgroups of interest both at baseline and during follow-up. Summary statistics such as means, medians, standard deviations, and ranges will be produced for measured variables, and compared within and between groups with chi-square, Student t-test/Wilcoxon test, or ANOVA analysis as appropriate. Graphical methods will be used extensively to examine distributions, identify potential influential points, and guide in data transformations if warranted.

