The majority of the choline present in egg yolks is found as part of phosphatidylcholine. We therefore hypothesize that the ingestion of phosphatidylcholine supplements will not elevate plasma TMAO levels to the same extent as a comparable amount of total choline ingested in capsule form as the choline bitartrate salt, but will instead elevate plasma TMAO levels in a comparable fashion to the whole eggs (hardboiled).

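### The plan expects phosphatidylcholine (PC) capsules to raise TMAO comparably to whole eggs, but it names only difference tests, which cannot support that half of a secondary hypothesis

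*Combined protocol and SAP*

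**What the plan says.** The last part of section 1.0 states a two-part hypothesis about PC. Set against choline bitartrate, "the ingestion of phosphatidylcholine supplements will not elevate plasma TMAO levels to the same extent". Set against eggs, PC capsules "will instead elevate plasma TMAO levels in a comparable fashion to the whole eggs (hardboiled". The first part predicts a difference and the second a similarity.

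Section 7.2 plans descriptive summaries (means, medians, SDs and ranges) and graphs. Its inferential content is that variables will be "compared within and between groups with chi-square, Student t-test/Wilcoxon test, or ANOVA analysis as appropriate". Section 7.1 states that "a sample size of 5 in each arm will provide us with a power of 0.9 to detect a significant difference between groups". Alpha there is 0.05. The section gives no effect size, SD, endpoint, test or sidedness.

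On numbers, section 6.0 sets out the study "with a goal of having at least 10 subjects complete each arm of the study", and section 3.0 allows enrolment "up to a maximum of 100 total study participants". On allocation, section 3.0 says that for the PC arm "subjects will not be randomized but will instead be assigned this arm until at least 10 subjects have completed this arm".

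Nowhere do the documents give a confidence interval for PC versus eggs, a margin, or a definition of comparable.

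**The concern.** Every method named in section 7.2 tests a null hypothesis of no difference. For PC versus bitartrate that is the right direction. For PC versus eggs it is not. A significant result would count against similarity, and a non-significant one could mean either that the two are alike or that the trial was too small to tell them apart. Neither result supports the prediction as stated.

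In a small study the ambiguous result is likely even when a moderate difference exists. The author of the report would then have a hypothesis of comparability, a non-significant test, and nothing in the plan to say that the second does not establish the first. The power in section 7.1 does not help, because it is the probability of finding a difference.

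**Working it through.** **Inputs.** Section 7.1: 5 per arm, power 0.9, alpha 0.05. Section 6.0: goal of at least 10 completers per arm. Section 3.0: maximum of 100 participants over 5 arms. The documents give no SD, so results are in units of the between-subject SD of the quantity analysed. A two-sided, unadjusted two-group t-test is assumed.

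**1. The plan's own figure.** The 5 per arm cannot be reproduced without an effect size, but the implied effect can be solved for. With df = 5 + 5 − 2 = 8 and SE = SD × √(1/5 + 1/5) = 0.632 SD, the noncentral t distribution gives power 0.9 at a difference of 2.35 SD (2.03 SD if the test is one-sided).

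**2. What a non-significant PC-versus-egg result allows at 10 per arm.**
- SE = SD × √(1/10 + 1/10) = 0.447 SD; df = 18; critical t = 2.101.
- Largest observed difference that is non-significant: 2.101 × 0.447 = 0.94 SD.
- Far end of the 95% CI at that point: 0.94 + 0.94 = 1.88 SD.
- Probability of a non-significant result (noncentral t): 82% for a true difference of 0.5 SD, 65% for 0.75 SD, 44% for 1 SD, 11% for 1.5 SD.
- Smallest true difference detected with power 0.9: 1.53 SD.
- Power for the 2.35 SD of step 1: 99.9%.

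Differences on the scale the trial appears to be sized for would therefore be found. Differences around 1 SD often would not.

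**3. Other numbers of completers.** The 20-per-arm row is an upper bound: 100 / 5 = 20, with an even split and no withdrawals, although section 3.0 says the large maximum is there to absorb withdrawals.

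| PC / eggs | SE (SD) | Non-significant up to (SD) | 95% CI can reach (SD) | True 1 SD missed |
|---|---|---|---|---|
| 10 / 10 | 0.447 | 0.94 | 1.88 | 44% |
| 10 / 20 | 0.387 | 0.79 | 1.59 | 30% |
| 20 / 20 | 0.316 | 0.64 | 1.28 | 13% |

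**4. Baseline adjustment.** Adjusting for the Day 1 value multiplies the SE by √(1 − ρ²), with df = 17 at 10 per arm. The correlation ρ is not in the documents. For assumed values of 0.3, 0.5 and 0.7 the non-significance limit falls from 0.94 to 0.90, 0.82 and 0.67 SD. Adjustment helps but does not remove the problem.

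**5. Would a formal equivalence test be realistic?** With two one-sided tests at 0.05 and a true difference of zero, 80% power at 10 per arm needs a margin of about 1.36 SD (unadjusted). A tighter margin would probably give an inconclusive result.

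**The case against.** The strongest case is one of proportion. The main goal in section 1.0 is whether supplement and egg choline differ. PC is an additional interest, and section 2.0 does not list comparability as an objective. Section 6.0 says: "This is a prospective pilot study consisting of 5 arms". The sentence on comparability can fairly be read as saying that PC behaves like eggs and not like bitartrate. The PC-versus-bitartrate and egg-versus-bitartrate tests, with the group summaries, speak to much of that. An unadjusted interval could also be computed later from the planned means and SDs. All of this stands, and it makes the point a secondary one. It does not supply a prespecified way to judge PC against eggs.

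It is also fair that the 1.88 SD limit lies below the effect implied by 5 per arm (2.35 SD, or 2.03 SD one-sided). A non-significant result at 10 per arm would argue against a gap that large. This stands, subject to the assumption about the test, and it confines the concern to moderate differences.

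A reader might infer three stronger things that the documents do not support:
- That the sponsor intends to read non-significance as comparability. No section says so; the plan is only silent.
- That 10 is a cap or a guaranteed floor. It is a goal in section 6.0, and section 3.0 fills the PC arm until at least 10 complete. More completers would narrow the interval and fewer would widen it.
- That the plan is deficient without an equivalence test. For a secondary expectation in a pilot, with no margin proposed, an interval and an honest label are enough.

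The non-randomised PC arm is disclosed in section 3.0. It is a separate limitation and adds no weight here, but the label on this contrast should carry it.

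**Conclusion.** The point holds in limited form. The inference planned in section 7.2 cannot support the PC-versus-egg half of the hypothesis, and the power in section 7.1 does not cover it. The PC-versus-bitartrate half is unaffected.

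The size of the gap depends on the completers reached and on the unadjusted two-sided t-test assumed above. At the goal of 10 per arm, true differences of about 1 SD would go undetected in more than two of five trials. Even at the 100-participant ceiling a non-significant result could leave differences of up to 1.28 SD open. It would be wrong to infer that any difference, however large, could pass unnoticed. The change is worth making because it costs little and closes off a misreading that the hypothesis invites.

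**What to change.** Add to section 7.2:

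> PC capsules versus whole eggs will be estimated as the ratio of geometric mean fasting plasma TMAO at the end-of-treatment blood draw (scheduled at Day 28), from a log-scale model adjusted for Day 1 TMAO, with a 95% CI. This comparison is descriptive and non-randomised because arm 5 is assigned, and a non-significant difference will not be reported as showing comparability.

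Add to section 7.1 that the 0.9 power is for detecting a difference and does not cover this hypothesis.

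With log Day 1 TMAO as the covariate, the arm ratio is the same whether the outcome is log Day 28 TMAO or its log change from Day 1: subtracting log Day 1 from both sides alters only the covariate's slope. The estimate therefore also compares the rise that section 1.0 describes. It does not replace the area-under-curve summaries in section 3.1. The section 3.0 schedule puts the last fasting draw at Day 28 and labels Day 29 the final visit, while the text places that draw at the final visit, so the added sentence should fix which draw is meant.

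No equivalence test is needed unless the sponsor fixes and justifies a margin before analysis.

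The cost is a few sentences. No extra participants or samples are needed, because both draws are already scheduled. The downside is that at about 10 per arm the interval will be wide, the conclusion on comparability will probably be only descriptive, and the estimate stays open to bias from the non-randomised arm.

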2.0 STUDY OBJECTIVES

To compare the blood and urine levels of free choline, phosphatidylcholine (PC), trimethylamine-N-oxide (TMAO), trimethylamine (TMA), and gammabutyrobetaine in subjects before versus following the ingestion of choline provided in either the bitartrate salt (in supplement) form, within phosphatidylcholine (in supplement form), within eggs (whole or in part), or in combinations of these.

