3.1 Study Endpoints

- Baseline plasma and urine fasting choline, phosphatidylcholine (PC), trimethylamine-Noxide (TMAO), trimethylamine (TMA), crotonobetaine and gammabutyrobetaine levels.
 - Changes in levels of non-labeled TMAO, TMA, crotonobetaine, betaine and gammabutyrobetaine over time measured by established techniques by mass spectrometry.
 - Baseline and subsequent (end of study blood draw) changes in platelet function during study.
- Serial changes in plasma and urine (area under curve and percent rise calculations).
 - Correlation with baseline fasting choline, phosphatidylcholine (PC), TMAO, TMA, crotonobetaine and gammabutyrobetaine levels.
- Changes in markers of metabolism (e.g. lipid profile, and other metabolic markers).

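### Section 7.2 leaves the TMAO outcome form open and does not use the pre-allocation baseline as a covariate; naming one form and adjusting for baseline on the log scale needs no new data

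*Combined protocol and SAP*

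**What the plan says.** Section 7.2 is the whole analysis plan. Measured variables are to be "compared within and between groups with chi-square, Student t-test/Wilcoxon test, or ANOVA analysis as appropriate", and any transformation is left to inspection of the data. The comparison is framed in section 2.0 as levels "in subjects before versus following the ingestion of choline", and section 3.1 lists changes over time next to "Serial changes in plasma and urine (area under curve and percent rise calculations"). None of these forms is designated for the comparison between arms. Baseline values appear as an endpoint and in an unspecified correlation, not as a covariate.

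The data for adjustment are already planned. Section 3.0 states: "At the first (baseline) study visit, subjects will have blood and urine samples collected". Allocation comes afterwards: "Subjects will then be randomized or assigned to one of the five study arms as described above". Later samples follow: "At the day 7 visit and the final visit they will have repeat blood and urine collections". On numbers, section 3.0 says "We expect to enroll at least 10 subjects into each of the 5 arms of the study, up to a maximum of 100" in total. For the phosphatidylcholine arm, "subjects will not be randomized but will instead be assigned this arm until at least 10 subjects have completed this arm".

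**The concern.** Two things are left undecided. The first is the outcome form and scale. Final level, change, percent rise and AUC can give different answers from the same samples, and the study is non-blinded, so an open form can be chosen after the results are seen. The second is the use of baseline. A change score removes baseline with a fixed slope of 1, and a follow-up-only comparison ignores it. ANCOVA estimates the slope, so it depends less on a correlation that nobody has stated.

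The stakes are highest for the subtler randomised contrast in section 1.0, bitartrate with versus without egg white, where only a smaller rise is hypothesised. With about 10 completers per arm, a precision gain that needs no extra sample is worth having.

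**Working it through.** **The plan's own figure.** Section 7.1 claims power 0.9 with 5 per arm at level 0.05, but gives no outcome, effect size or SD. It can only be solved backwards: a two-sided t-test needs a standardised difference of 2.35. The documents neither confirm nor refute that, and it supplies no SD for what follows.

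**Inputs.** From the documents: 10 per arm, level 0.05, and blood at baseline, day 7 and the end. Assumed, because the documents are silent: two-sided testing, log-normal TMAO, equal log SD 0.7 at each time, a true 2-fold ratio, and baseline-to-final log correlation r from 0 to 0.8.

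**Variance of a two-arm contrast, relative to follow-up only = 1.**
- Log change: 2(1 − r).
- ANCOVA, two arms of 10 (17 error df): (1 − r²)(1 + 1/16).

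At r = 0.4 these are 2 × 0.6 = 1.20 and 0.84 × 1.0625 = 0.89. At r = 0 they are 2.00 and 1.06. At r = 0.9 both are about 0.20.

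**95% CI factor for the geometric mean ratio at r = 0.4, exp(t × SE).**
- Follow-up only: SE = 0.7 × √(2/10) = 0.313; t(18 df) = 2.101; factor 1.93.
- Log change: SE = 0.313 × √1.20 = 0.343; factor 2.06.
- ANCOVA: SE = 0.313 × √0.8925 = 0.296; t(17 df) = 2.110; factor 1.87.

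**Power, 2-fold ratio** (40,000 simulated two-arm trials per setting):

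| r | 0 | 0.2 | 0.4 | 0.6 | 0.8 |
|---|---|---|---|---|---|
| Percent-rise t-test | 20% | 27% | 37% | 56% | 88% |
| Percent-rise Wilcoxon | 28% | 34% | 44% | 60% | 88% |
| Log change | 32% | 38% | 48% | 65% | 91% |
| Log follow-up only | 55% | 55% | 56% | 55% | 56% |
| Log final value, ANCOVA | 53% | 54% | 60% | 72% | 92% |
| Log AUC, unadjusted* | 80% | 71% | 64% | 58% | 53% |
| Log AUC, ANCOVA* | 78% | 75% | 77% | 85% | 98% |

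*AUC over days 1, 7 and 28, with the full effect assumed present from day 7.

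Simulation error is about half a point; the exact value for follow-up only is 55% at every r. Within a form, adjustment loses up to 3 points (final value) or 2 points (AUC) at r = 0. It gains from r = 0.4 upward for the final value and from r = 0.2 for AUC.

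**Sensitivity to SD.** At r = 0.4 the gain of ANCOVA over follow-up only is 2 points at SD 0.4, 5 at SD 0.7 and 3 at SD 1.0.

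**Large effect.** For a 10-fold rise against none (SD 0.7 to 1.0, r 0.2 to 0.4), a percent-rise t-test has 64–98% power and every other form at least 94%.

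**Unequal spread.** Take follow-up log SD 1.0 in bitartrate arms and 0.5 in the others, with no true effect. A four-arm ANCOVA with one pooled variance gives 6.8–7.7% false positives for bitartrate with versus without egg white. Two-arm models give 4.8–5.1%. For bitartrate versus eggs at 10 v 20 subjects, the equal-variance model gives 10.9–11.5%, and arm-specific variances with Satterthwaite df stay at 4.7–5.5%.

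**The case against.** **Change scores and logs are already allowed.** This stands. The plan does not ignore baseline and does not forbid a log scale. The gap is that nothing is chosen and no covariate is named.

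**A reader might infer that ANCOVA on the final value beats every listed form.** It does not. If the effect is full by day 7, unadjusted log AUC beats it by 27, 17 and 4 points at r 0, 0.2 and 0.4. If the effect appears only at the last visit, unadjusted AUC falls to about 30%, 25% and 22% at those correlations and the order reverses. The documents do not give the time course, so they cannot settle which form is best.

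**ANOVA pooled over four arms is a stronger comparator than a two-arm test.** With equal spreads this holds. Pooled ANOVA on log follow-up (36 df) has 57.7% power, against 52.9%, 54.5% and 59.7% for two-arm ANCOVA at r 0, 0.2 and 0.4. At r = 0.8, pooled ANOVA on log change has 92.6% against 92.0%. The gain over the better existing option is then confined to mid-range correlation. Pooling loses its protection against false positives when spreads differ.

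**It is a pilot.** Section 6.0 says so, and that limits the weight of the point. But section 1.0 states directional hypotheses and section 7.1 claims power for a between-group difference.

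**A reader might infer a false-positive rate of 10–11%.** That is the rate from taking the smallest p over four forms (percent-rise t and Wilcoxon, log change, log follow-up). It is a worst case, and nothing in the documents says the form will be picked that way.

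**A reader might infer that the baseline correlation endpoint is flawed.** Change correlated with its own baseline is negative through regression to the mean alone. Section 3.1 does not say what is correlated, so the point does not rest on this.

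**Conclusion.** The point holds as an inexpensive improvement that should be made. The plan fixes no lead outcome form and leaves unused, as a covariate, a baseline value that every subject provides before allocation. For a given form, baseline adjustment on the log scale costs at most about 3 points of power when r is near zero and gains at moderate to high correlation. Its main merit is robustness to an unknown r: log change does badly at low r and follow-up only at high r.

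The size is conditional. SD, correlation, distribution and the 2-fold target are all assumptions, and at r = 0.4 the CI factor moves only from 1.93 to 1.87. For bitartrate versus eggs, if the 10-fold rise in section 1.0 recurs and eggs show none, the gain is negligible except against a raw percent-rise t-test.

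The precision argument covers the four randomised arms only. For the phosphatidylcholine arm, ANCOVA and change scores can estimate different quantities. With a 1 SD baseline gap that would have persisted untreated, ANCOVA is off by 1 × (1 − r), which is 0.5 SD at r = 0.5. Adjustment does not remove confounding there.

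**What to change.** Add to section 7.2, before the data are seen:

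- One lead outcome form and scale for plasma TMAO: log final value, or log AUC if an early, sustained effect is expected.
- Comparison of the randomised arms by ANCOVA on that outcome with log baseline TMAO as covariate and arm-specific variances (Satterthwaite df), for example one two-arm model per planned contrast.
- Geometric mean ratios with 95% CIs. Percent rise is kept as description.
- Contrasts with the phosphatidylcholine arm labelled non-randomised, with a note that ANCOVA and change scores may answer different questions there.
- A rule for values below the assay limit, which the log scale requires.

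The cost is a few lines of text and code, and no new samples. Statistically, the slope uses one degree of freedom, and up to 3 points of power are lost if r is near zero. Two-arm models lose 2–4 points to a pooled four-arm ANCOVA, and up to 5 to pooled ANOVA at low r, if spreads are equal. Arm-specific variances cost up to 0.5 points more. Choosing final value over AUC gives up power if the effect is full by day 7 and gains power if it is late, so the choice should be argued in the plan. Naming one form does not settle multiplicity across several contrasts.
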